The margins to be given to tumour bed for defining boost field have also been discussed. Harrington et al¹⁴ have shown that a boost field marked on the basis of clinical data and background with a margin of 2 cm all around covers radiological field with same margin in only 1/3rd (33%) of patients. Although Vicini et al. showed that a margin of 1 cm around the tumour covers microscopic disease adequately, in EORTC trial margins of 1.5 cm were given for microscopically completely excised tumours. Overall, a margin of 1.5-2 cm to the tumour bed has been reported to cover all subclinical disease in patients with clear microscopic margins.

Some institutions have practised tumour bed boost by 4-6 MV photons. The practice of delivering boost by photons has declined after widespread availability of electrons due to

higher penetration and increased doses to underlying critical structures. Photons can be used in patients with small tumour bed as late term sequelae of electrons such as telangiectasia may not be acceptable to some patients treated with electrons.

Aims and Objectives: Primary objective- To evaluate dosimetric outcomes in tumor bed boost irradiation in patients undergoing breast conservative surgery using three different surgical techniques

Secondary objective-Evaluation of cosmesis in patients prior to radiotherapy, at the time of completion of radiotherapy and 6 months post completion of radiotherapy

Material and methods-

Patients will be screened for the study at the time of radiotherapy simulation for External beam radiotherapy

The sample size has not been calculated as this is a pilot study. Twenty patients will be accrued for the purpose of this study. The patients will be divided into three groups:

Group A- Patients who underwent open cavity BCS

Group B- Patients who underwent closed cavity BCS

Group C- Patients who underwent oncoplasty

Inclusion Criteria- All patients undergoing Breast Conservative Surgery (Open Cavity/Closed Cavity) or Oncoplasty will be eligible for this study.

Exclusion Criteria-1. Patients undergoing Neoadjuvant chemotherapy will not be eligible for the purpose of this study.

2. All patients undergoing Modified Radical Mastectomy will not be eligible for the purpose of this study

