Informed consent will be taken for all patients at the time of Radiotherapy simulation. All patients will first receive external beam Radiotherapy to the whole breast to a dose of 40Gy/15#/3weeks. The patients will then be planned for boost radiation to the tumor bed to a dose of 12.5 Gy/5#.

The combination of surgical clips with a treatment planning CT scan for the lumpectomy site for electron boost and to determine the appropriate energy will be used for tumour bed boost delineation

For the boost planning CT scan a small thermocol wedge will be used, with a pillow under the shoulder to make the surface as flat as possible.

The pT size in HPR of lumpectomy plus a margin of 2 cm in all directions is the approximate size of the boost field. The margins of this field are marked on the skin with the centre of scar as the center of the field and copper wire is placed on the markings.

5 mm slice thickness CT scan will be taken in the treatment position. After the scan acquisition the data will be transferred to the Varian Eclipse treatment planning system.

The post-operative cavity depicted on the CT images will be contoured section by section. All available images will be assigned a cavity visualisation score⁹ (CVS) as per the British Columbia Cancer Agency Cavity visualisation score 0-No visible seroma, 1-scar/shadow, 2-seroma identifiable but with significant (>30%) uncertainties, 3-seroma identifiable with minor (<30%) uncertainties, 4- seroma easily identifiable, generally homogenous with some blurring of margin, 5-seroma clearly identifiable, homogenous with sharp boundaries. The mean cavity visualisation score will be determined for each group of patients.

The CTV will be generated by using a 15 mm uniform expansion from the lumpectomy cavity but limited by skin and chest wall. The CTV will be extended by an additional 10 mm uniform expansion to generate the PTV

Treatment plans for tumor bed boost irradiation will be made using both electrons and photons with 3DCRT technique for each patient and comparison will be made for various dosimetric variables. The photon beam plan will only be generated for purposes of dosimetric study and will not be used for treatment of the patients

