The following dosimetric variables will be determined for each patient -seroma cavity volume (ccs). PTV volume (ccs). In addition the ratio between the PTV volumes to the whole breast volume will be determined. The Radiation Conformity Index (RCI) will be determined for both set of plans. It was first defined by Knoos et al and a revised definition appeared in ICRU 62 It is the ratio of volume of the PTV to the volume that receives 95% prescribed dose or higher ($RCI = V_{PTV} / V_{95\%}$). The Dose Homogeneity Index (DHI) will be determined for both set of plans (DHI). It is ratio of dose received by 95% of PTV volume to the dose received by 5% of PTV volume ($DHI = D_{\geq 95\%(\text{within PTV})} / D_{\geq 5\%(\text{within PTV})}$). The dose received by several normal structures will be determined for both set of plans-normal ipsilateral breast tissue (Whole breast volume- PTV volume), contralateral breast, ipsilateral lung, contralateral lung and heart

The borders of the portal will be modified based on the position of the lumpectomy cavity/seroma of the scan and marked on the patient. The boost irradiation for all patients will be done using electrons. The energy of electrons required will be decided from the depth of the lumpectomy cavity.

In addition the cosmesis will be determined for all the patients prior to starting radiotherapy, at the time of conclusion of radiotherapy and 6 months post completion of radiotherapy. This will be done by using the criteria suggested by Harris et al

1. Excellent: the treated breast almost identical to the untreated one.
2. Good: the treated breast slightly different from the untreated breast.
3. Fair: obvious difference between the two sides without major distortion.
4. Poor: the treated breast is seriously distorted.

Statistical analysis shall be performed with the Statistical Package for Social Sciences (SPSS, Chicago, IL) software package, version 21.0, for Windows A two-tailed PValue less than 0.05 will be considered as statistical significance in this study. Descriptive statistics, including frequency distributions, means \pm SD, and 95% confidence intervals, to be calculated for demographic and treatment variables. The statistical analysis will be carried out using the One way ANOVA or Krsukal Wallis test and categorical comparison will be done using Chi Square test.

References:

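### No analysis is specified for the paired electron–photon comparison or for whether it varies by surgical technique, and setting two separate p-values side by side would not supply one

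*Combined protocol and SAP*

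**What the plan says.** The primary objective (Aims and Objectives) is "To evaluate dosimetric outcomes in tumor bed boost irradiation in patients undergoing breast conservative surgery using three different surgical techniques". On size, Material and methods says "Twenty patients will be accrued for the purpose of this study" and "The sample size has not been calculated as this is a pilot study". On structure it says "The patients will be divided into three groups": open cavity, closed cavity and oncoplasty. Group sizes are not given.

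The treatment-planning text then adds a second, within-patient factor: "Treatment plans for tumor bed boost irradiation will be made using both electrons and photons with 3DCRT technique for each patient". It also promises to set the two plans against each other on a range of dosimetric measures, and names no method there. The photon plan is for dosimetric study only and is not delivered. The conformity index (RCI), the homogeneity index (DHI) and the doses to five normal structures (ipsilateral breast outside the PTV, opposite breast, each lung, heart) are obtained from both plans. That makes seven paired variables.

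The statistical paragraph says "The statistical analysis will be carried out using the One way ANOVA or Krsukal Wallis test", with chi-square for categorical data, and "A two-tailed PValue less than 0.05 will be considered as statistical significance in this study". It names no paired test, repeated-measures or mixed model, or technique-by-modality analysis, and it has no multiplicity rule.

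**The concern.** The data form a three-by-two layout: technique between patients, modality within patients. The named tests take one factor with independent observations. This leaves two things unspecified.

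1. **The announced electron–photon comparison.** A one-way test that treats the two plans of one patient as independent discards the pairing.
2. **Whether that difference depends on technique.** A three-group one-way test most naturally means testing technique once in the electron values and once in the photon values. A reader who sees significance in one set only may conclude that technique matters more for that modality. Two p-values on opposite sides of 0.05 do not support this. An overall electron–photon test does not help either, because it averages over technique.

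At stake is a published statement about modality and surgery that rests on a chance split, or a real dependence that goes unexamined although the data to examine it were collected.

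**Working it through.** **Nothing to reproduce.** The 20 patients come without power, effect size or SD.

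**Inputs from the documents.** N = 20; three groups; two plans per patient; two-sided 0.05 per test; seven paired variables.

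**Assumed, because the documents do not say.** Groups of 7/7/6 (10/7/3 and 12/5/3 gave discordance within about 1 point in the Cohen's f scenarios below); normal data with equal SD in the two modalities; within-patient correlation ρ from 0.3 to 0.9.

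**Step 1: cost of ignoring the pairing.** With common SD σ, the variance of the within-patient difference is 2σ²(1−ρ); treating the plans as independent uses 2σ². The standard error is overstated by 1/√(1−ρ): 1/√0.7 = 1.20 at ρ = 0.3, 1/√0.5 = 1.41 at ρ = 0.5, and 1/√0.1 = 3.16 at ρ = 0.9.

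**Step 2: how often two separate tests split with no interaction.** The same technique effect is placed in both modalities. For a 1.2 SD shift of the six-patient group, noncentrality is 20 × 0.3 × 0.7 × 1.2² = 6.05 on F(2,17), so each test has about 51% power. Simulated proportion of trials in which exactly one of the two tests is significant:

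| ρ | no technique effect | 1.2 SD effect in both |
|---|---|---|
| 0.3 | 9% | 42% |
| 0.5 | 8% | 36% |
| 0.7 | 7% | 28% |
| 0.85 | 5% | 20% |
| 0.9 | 5% | 16% |

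A 1.2 SD shift lies near the peak, because splits are most frequent at about 50% power. Over other effect sizes (Cohen's f) at ρ = 0.5, the figure is 19% at f = 0.25, 30% at 0.4, 35% at 0.5, 29% at 0.7, 12% at 0.9 and about 1% at 1.2.

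**Step 3: the direct test.** Let d = electron minus photon for each patient. A one-way ANOVA of d across the three groups is the technique-by-modality interaction test. In the same scenarios it was falsely significant about 5% of the time.

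**Step 4: its power.** If the 1.2 SD effect is present in one modality only, noncentrality is 6.05 / [2(1−ρ)]: 4.32, 6.05, 10.08 and 20.16 at ρ = 0.3, 0.5, 0.7 and 0.85. Power is 38%, 51%, 74% and 96%. By effect size on the difference scale, power is 14% at f = 0.25, 29% at 0.4, 59% at 0.6, 73% at 0.7 and 84% at 0.8.

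**Step 5: multiplicity.** Seven such tests at 0.05, if independent, give 1 − 0.95⁷ = 30% chance of at least one false positive.

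**The case against.** The strongest reply is that the documents never ask whether technique changes which modality is better. The objective concerns dosimetry across three techniques, the photon plan is never delivered, and this is a 20-patient pilot. That stands: no declared aim fails for want of an interaction analysis. It does not answer the other half, because the electron–photon comparison is announced in the plan and has no method suited to paired data.

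Three stronger readings are tempting, and the documents do not support them:

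- *That the modalities will be tested separately.* This is an inference. The statistical paragraph names tests without saying what each is applied to.
- *That the study cannot address modality by technique.* It can. Both plans exist for every patient, and the named one-way test applied to the differences would do it.
- *That the report will claim modality should depend on surgery, or that the two tests will usually disagree.* No such claim is planned. The split rate is high only for a moderate technique effect with low to moderate correlation.

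A fair objection also applies to the remedy. The background describes minimal dose to underlying normal structures with electrons and higher dose with photons, so the two scales may differ greatly for organ doses. If the electron scale were one fifth of the photon scale (assumed) and the 1.2 SD standardised effect identical, the difference test would be significant in about 40–47% of trials at ρ from 0.5 to 0.85. It would largely repeat the photon result. That is a genuine difference in absolute dose, but not in standardised effect, so the scale must be declared.

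**Conclusion.** The gap is real and limited. A paired comparison is promised with no paired method, and no analysis is given for whether the electron–photon difference varies by technique. If separate tests are run and their p-values compared, a split with no true interaction is expected in about 5–9% of trials without a technique effect and about 16–42% at a 1.2 SD effect (ρ from 0.9 down to 0.3). It falls to about 1% for a very large effect. These figures rest on assumed group sizes, normality, equal SDs, effect sizes and correlations, none of which the documents give. The point is worth correcting because the remedy is small. It does not show a flaw in the design or a failed objective.

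**What to change.** Add to the statistical paragraph:

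> For DHI, each organ dose and the distance of RCI from 1, the electron-minus-photon difference will be computed for each patient and reported overall (paired analysis) and by surgical group with 95% confidence intervals. Differences will be compared across groups with the same one-way test, as an exploratory analysis on the absolute scale. Any statement that the effect of technique depends on modality will rest on this analysis, not on comparing the p-values of the two plan sets.

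Distance from 1 is used for RCI because this ratio of PTV to the 95%-dose volume can depart from 1 in either direction.

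Cost: one derived variable per outcome, slightly more analysis and no new data. With 20 patients, power is low unless the interaction is large, so estimates and intervals should lead. The seven tests carry no multiplicity control and should not be read as confirmatory. For organ doses, the report should say that a difference on the absolute scale may reflect the larger scale of one modality.

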Thus, in breast cancer patients who have undergone oncoplastic surgery, the tumor bed is frequently more extensive and possibly more relocated compared to original presentation. Placement of surgical clips after tumor resection and before oncoplastic reconstruction may be the most accurate method to localize the RT local boost field^{12, 13}.

Techniques of Radiotherapy boost delivery-Variou techniques of tumor bed boost delivery have been extensively studied and their efficacy compared retrospectively and prospectively. The various techniques are electrons, photons(less commonly used due to higher penetration and increased doses to critical underlying structures) and interstitial brachytherapy (i.e. interstitial placement of needles into tumor bed either intraoperatively or postoperatively)

With most of the centres now having linear accelerators, coronal en face electron beams have now become standard practice in most institutions. Minimal dose to underlying normal structures, i.e. lung and breast to the maximum, varying energy of electrons, feasibility of defining field on skin, an outpatient procedure with minimal patient discomfort make it a favourable option for both the patient as well as treating radiation oncologist. Most commonly used energies are 9-12 MeV. However, the boost fields defined on the basis of clinical details have been found to be erroneous in several studies. Hence, the dimensions as well as depth for tumour bed boost should be determined either by fluoroscopy or CT combined with surgical clips, or an ultrasound. The most common prescription isodose for electron boost delivery is 90-95% isodose. But, in an organ such as breast with multiple edges and curvatures in different axes, the prescription isodose may not cover the whole target volume uniformly. This problem is commonly seen when tumours are located at areas where there is a sudden change in the depths like inframammary and axillary folds. The depths of soft tissue vary greatly in these areas and uniform energy electron beam may either underdose the tumour bed, or deliver higher dose to underlying normal structures. The electrons have limited role in patients with large breasts, tumours situated at a depth i.e. closer to heart (on left) and lungs and in folds. CT based planning in three dimensions may help to determine the dose distributions accurately and help in choosing the optimal energy.

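### The listed dosimetric variables include no measure of PTV coverage and no PTV dose relative to the 12.5 Gy prescription, and RCI and DHI together do not supply either

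*Combined protocol and SAP*

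**What the plan says.** Aims and Objectives makes dosimetric outcomes across three surgical techniques the primary objective. Under Material and methods, the boost prescription is 12.5 Gy in 5 fractions. An electron and a photon plan are made for each patient, and "comparison will be made for various dosimetric variables".

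The variables then listed are cavity volume, PTV volume, the ratio of PTV to whole breast, RCI, DHI, and the dose to five normal structures. RCI is V_PTV/V_95%: "It is the ratio of volume of the PTV to the volume that receives 95% prescribed dose or higher". DHI is D95%/D5%: "It is ratio of dose received by 95% of PTV volume to the dose received by 5% of PTV volume". The DHI formula is marked as applying within the PTV; the RCI formula carries no such mark.

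On target volumes, the CTV is a "15 mm uniform expansion from the lumpectomy cavity but limited by skin and chest wall". Then "The CTV will be extended by an additional 10 mm uniform expansion to generate the PTV", with no skin or chest-wall limit stated for that second step.

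The analysis will be carried out "using the One way ANOVA or Krsukal Wallis test and categorical comparison will be done using Chi Square test".

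The background on boost delivery techniques warns that in the breast "the prescription isodose may not cover the whole target volume uniformly", and that in folds a "uniform energy electron beam may either underdose the tumour bed, or deliver higher dose to underlying normal structures". It adds that three-dimensional CT planning may help.

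**The concern.** Of the listed variables, the volumes and the volume ratio contain no dose, and the normal-structure doses do not concern the target. Only RCI and DHI are left to describe target dose. Neither states what share of the PTV reaches 95% of prescription, or what the PTV receives relative to 12.5 Gy.

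The study could therefore report differences in RCI and DHI between surgical groups, or between electron and photon plans, without saying whether the target received its dose. A lower DHI can mean a cold target or a hot spot. At RCI of 1 or below, a change in RCI can mean a tighter field or lost dose. The protocol's own background raises incomplete cover and electron underdosage as issues, yet no listed variable would show whether they occur in these plans.

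**Working it through.** The plan gives no figure to reproduce here, and the sample size was not calculated. The check is algebra, followed by constructed examples.

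**Inputs from the protocol.** Prescription 12.5 Gy; threshold 0.95 × 12.5 = 11.875 Gy; the RCI and DHI formulas above.

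**1. RCI.** Coverage is the PTV volume at or above 11.875 Gy, divided by V_PTV. The covered part cannot exceed V_95%, so coverage ≤ min(1, V_95%/V_PTV) = min(1, 1/RCI).
- RCI 1.1: coverage at most 91%.
- RCI 1.3: coverage at most 77%.
- RCI 1 or below: no limit. For example, if the PTV and the 95% volume are equal 5 cm cubes (RCI = 1.0) displaced by 1 cm along one axis, coverage is (5 − 1)/5 = 80%; with no displacement it is 100%.

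**2. DHI.** If all doses are multiplied by c, then cD95%/cD5% = D95%/D5%. For DHI 0.85:
- D5% = 100% of prescription (12.5 Gy) gives D95% = 0.85 × 12.5 = 10.6 Gy. Less than 95% of the PTV reaches 11.875 Gy.
- D5% = 115% (14.4 Gy) gives D95% = 97.75% (12.2 Gy). At least 95% of the PTV does.

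**3. Both indices held equal.** Assumptions, none from the protocol: spherical PTV, plateau dose 102%, Gaussian penumbra with sigma 0.5 cm, field size solved for RCI 0.80. An off-centre field is compared with a centred field whose hot gradient is solved to give the same DHI. PTV radius 4 cm:

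| Off-centre by | DHI (both plans) | Coverage, off-centre | Coverage, centred | D5% of centred plan |
|---|---|---|---|---|
| 1 cm | 0.86 | 90% | 100% | 121% |
| 0.5 cm | 0.97 | 98.5% | 100% | 105% |

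Over radii of 3 to 5 cm, coverage of the off-centre plan is 84% to 94% (1 cm) or 96% to 99.6% (0.5 cm). The centred match stays at 99.7% or above.

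**4. A case where RCI helps.** With radius 4 cm, plateau 103%, sigma 0.6 cm and field radius 5.2 cm, scaling the whole plan by 0.93 leaves DHI at 0.983. Coverage falls from 100% to 83% and D95% from 101% to 94% of prescription. RCI moves from 0.78 to 1.20, which does signal the loss.

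**5. Why the evaluation volume must be defined.** The 10 mm expansion can carry the PTV outside the skin. Assume flat skin, a spherical cavity of radius 1.5 cm, no chest-wall limit, and zero dose outside the body. The share of PTV in air is then 12%, 8%, 4% and 0% for a cavity edge 0.5, 1.0, 1.5 and 2.5 cm deep. With assumed radii of 0.5 to 2.5 cm, the range at 0.5 cm depth is 19% to 8%. Once that share exceeds 5%, D95% of the whole PTV falls in air and says nothing about the target.

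**The case against.** The strongest reply is that this is an omission, not a mistake. The plan never claims that RCI or DHI measures coverage; both are clearly defined and computable. D95% must be calculated to form DHI, so the data will exist, and this is a 20-patient pilot. All of that stands. It makes the remedy cheap, but the listed outcome is still only the ratio.

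A second reply is that the practical size is unproven. That also stands. The larger gap in the matched pairs needs a 1 cm miss, although the protocol has the portal borders adjusted to the cavity position, and it needs a comparator with D5% of 121%. The milder pair differs by only 1.5 percentage points, and in the scaling case RCI gives the warning.

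A third is that V_95% might mean only the part of the PTV above the threshold. RCI would then equal 1/coverage and would identify it. The wording does not say so, and the within-PTV mark on DHI alone points to the whole-volume reading.

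A reader might infer that the electron plans will underdose the target, or that the indices are invalid. The documents support neither: the background names underdosage as a possibility and CT planning as a help, and no plan results are given. Nor would a PTV measure detect a wrongly delineated tumour bed, since it scores the plan against the contour as drawn.

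**Conclusion.** The gap is real and follows from the definitions alone. No listed variable gives PTV coverage or PTV dose relative to prescription, and RCI with DHI does not identify either, except that RCI above 1 shows some under-coverage. The constructed cases demonstrate non-identifiability; they rest on assumed shape, penumbra, gradient and displacement and do not forecast a difference in this study. The size of any real effect is unknown. The change is worth making because the primary objective is dosimetric, the protocol itself raises the question, and the added figures come from plans already to be made.

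**What to change.** In the dosimetric variables paragraph of Material and methods, for both the electron and the photon plan:

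- Add (1) the percentage of PTV receiving at least 95% of the prescribed dose and (2) D95% as a percentage of prescription. Interpret RCI and DHI only beside them.
- State one PTV evaluation volume, the part of the PTV inside the body contour, for scoring only. Use it for every PTV-based quantity: PTV volume, PTV/breast ratio, RCI, DHI, coverage, D95%, and normal breast as whole breast minus PTV.
- Note that the 10 mm expansion is not limited by the chest wall either, so low PTV coverage deep to it need not mean an underdosed tumour bed.
- Report the additions by surgical group with medians and ranges, using Kruskal-Wallis if tested. Report the electron-photon contrast as a within-patient difference (median and range; Wilcoxon signed-rank if tested), because both plans come from the same patient and the analysis paragraph names only tests for independent groups.
- Label all of this exploratory.

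Cost: one cropped evaluation structure per patient, a few lines of definition, and two more outcomes. If every contrast is tested, that is 2 measures × 2 plans by group plus 2 paired = 6 tests. At 0.05 each, and if independent, the chance of at least one false positive is 1 − 0.95^6 = 26%, which is why description should come first. No change to planning, energy choice or treatment is involved.

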Computed tomography and ultrasonography can use the seroma as a surrogate for tumor bed position, but there are limitations. First, the seroma is only clearly defined in only about quarter of patients. Second the seroma underestimates the tumor bed defined by implanted clips.

Uncertainty in localising the tumor bed in medial or lateral tumors can be overcome by increasing the posterior field borders of whole breast tangents, but only at expense of increased morbidity of ribcage and lung, and potential mortality in women with left sided tumors. The heart is the most sensitive organ, a few Gy being associated with risk of heart disease and every effort needs to be made to exclude the organ from treatment volume. When localising the tumor bed boost, increasing the clinical target volume is a crude way of avoiding geographical miss. This is particularly important in the era of oncoplastic surgery when the tumor bed may be well away from its primary location.

Accurate delineation of the target volume is of utmost importance while delivering tumour bed boost with external beam radiotherapy. Different institutions use different methods for delineation of the tumour bed.

Clinical history and patients' recollection of tumour position, clinical photographs, tattoos, surgical scar, mammography, surgical clips, ultrasonography, Computerized tomography

(CT) scan and Magnetic resonance imaging (MRI) are the commonly utilized techniques. Many a times, a combination of one or more of these techniques is considered while delineating the tumour bed boost.

Amongst all the randomised trials assessing role of radiotherapy boost, surgical clips were used in all patients for assessing boost volume only in the Budapest trial⁸. In other studies, the boost volumes were usually defined on clinical and surgical details. It was hypothesized that increasing differences between local failure rates in whole breast radiotherapy (WBRT) arm versus WBRT+boost arm in Lyon trial (4.5% vs. 3.6%), EORTC trial (10.2% vs. 6.2%) and Budapest trial (15.5% vs. 6.7%) [may well have been due to the different techniques of tumour bed delineation as the difference in boost doses between all these trials were not significantly different. Hence an accurate delineation of tumour bed is important as it may translate into improved local control rates.

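### The tests named for continuous outcomes cannot hold treated side, so a left-right gap in heart dose would add avoidable noise to the comparison of surgical groups (minor)

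*Combined protocol and SAP*

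**What the plan says.** All references are to the combined protocol and SAP.

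- **Aims and Objectives.** The primary objective is "To evaluate dosimetric outcomes in tumor bed boost irradiation in patients undergoing breast conservative surgery using three different surgical techniques".
- **Material and methods, sample size and groups.** "Twenty patients will be accrued for the purpose of this study". The number is declared as not calculated because the study is a pilot. Patients fall into three groups by the surgery they had. Group sizes are not given.
- **Inclusion Criteria.** "All patients undergoing Breast Conservative Surgery (Open Cavity/Closed Cavity) or Oncoplasty will be eligible for this study". Treated side is not mentioned.
- **Material and methods, dosimetric variables.** Doses to normal structures are determined for both electron and photon plans. The list covers normal ipsilateral breast and then "contralateral breast, ipsilateral lung, contralateral lung and heart".
- **Material and methods, treatment plans.** Electron and photon plans are made for each patient and "comparison will be made for various dosimetric variables".
- **Material and methods, statistical analysis.** One-way ANOVA or Kruskal-Wallis is named, with chi-square for categorical comparisons, at a two-tailed 0.05 level. The sentence does not say which outcome or comparison each test serves. Descriptive statistics include frequency distributions and "95% confidence intervals, to be calculated for demographic and treatment variables". No covariate, stratification or display by side appears.
- **Background.** The text on tumour bed localisation speaks of "potential mortality in women with left sided tumors. The heart is the most sensitive organ". The text on boost techniques says electrons have a limited role in, among others, "tumours situated at a depth i.e. closer to heart (on left) and lungs and in folds".

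**The concern.** Labelling breast and lung as ipsilateral or contralateral builds side into those variables. The heart is a single organ with no such label, so its recorded dose mixes left-sided and right-sided treatments. The protocol's own background gives reason to expect these to differ.

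A one-factor test leaves that difference unmodelled. When side is balanced across groups, the whole gap sits in the within-group variation. When side is imbalanced in a given sample, part of it also enters the group contrast. At stake is mainly precision: with 20 patients, a real effect of surgical technique on heart dose would be harder to see than it need be. A spurious technique difference is a lesser risk, arising in samples where side happens to be imbalanced, or if side is related to technique, which no document shows.

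**Working it through.** **There is no stated figure to reproduce.** The plan gives no power and no calculated sample size.

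**Inputs from the documents:** 20 patients, three non-randomised groups, two-sided 0.05, one-way ANOVA or Kruskal-Wallis, no restriction on side.

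**Assumptions (not in the documents):** groups of 7/7/6; 50% left-sided, unrelated to technique; normal errors with within-side SD of 1; left-right gap *g* of 0 to 4 SD; technique effects of 0, 0.75 and 1.5 SD.

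**Step 1, formula.** With left-sided share *p* balanced across groups, omitting side multiplies the error variance by 1 + g²p(1 − p). At p = 0.5 this is 1 + g²/4:

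| g (SD) | Variance factor | SE factor | 20 patients are worth |
|---|---|---|---|
| 0.5 | 1 + 0.25/4 = 1.06 | 1.03 | 18.8 |
| 1 | 1 + 1/4 = 1.25 | 1.12 | 16.0 |
| 2 | 1 + 4/4 = 2.00 | 1.41 | 10.0 |
| 3 | 1 + 9/4 = 3.25 | 1.80 | 6.2 |

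**Step 2, simulation with side assigned at random** (40,000 replicates per setting). The half-width is the mean for the 95% CI of the third minus the first group.

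| g (SD) | ANOVA power, no side | ANOVA power, with side | Half-width, no side | Half-width, with side | Kruskal-Wallis power |
|---|---|---|---|---|---|
| 0 | 59% | about 56% | 1.16 | 1.20 | 53% |
| 0.5 | 57% | about 56% | 1.19 | 1.20 | 51% |
| 1 | 49% | about 56% | 1.29 | 1.20 | 44% |
| 2 | 32% | about 56% | 1.64 | 1.20 | 27% |
| 3 | 20% | about 56% | 2.10 | 1.20 | 17% |
| 4 | 14% | about 56% | 2.61 | 1.20 | 14% |

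ANOVA on ranks with side has 55% power, falling to 51% as the gap grows. Part of its advantage over Kruskal-Wallis is a difference in test size: 5.1–5.3% type I error against 4.3–4.5%.

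**Step 3, type I error.** With side unrelated to technique, ANOVA has 5.0–5.4% without side and 4.7–5.0% with it. If left-sided shares were 40/50/60% by group (hypothetical), it would be 5.7%, 7.0%, 7.9% and 8.5% at gaps of 1 to 4 SD without side, and about 5% with it.

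**Step 4, technique acting on the left only.** With right-sided SD of 0.2 and gaps of 1 to 4 SD, power is 14%, 10%, 8% and 8% without side, 21–22% with side, and about 25% in left-sided patients alone.

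**Step 5, would summaries by group and side suffice?** Exact binomial counts at 50% left-sided:

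- All cells have at least 2 patients with probability 0.875 × 0.875 × 0.78125 = 0.598, so some cell has 0 or 1 in 40% of samples (51% at 40% or 60% left-sided).
- All cells have at least 3 with probability 0.546875² × 0.3125 = 0.093, so some cell has fewer than 3 in 91%.
- Some group has no left-sided patient with probability 1 − (127/128)² × (63/64) = 0.031. A left-sided median is therefore available for all three groups in 97%.

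**The case against.** The strongest objection is that the documents do not show a gap large enough to matter. They give no heart-dose SD, no left-right difference and no laterality mix. The gain from adjustment is nil at gaps of 0 to 0.5 SD and large only from about 2 SD. The background remark on left-sided mortality concerns widening whole-breast tangents, not the boost; the remark on electrons does concern the boost but is qualitative and about deep tumours. All of this stands, and it is why the size can only be given as a range.

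Two inferences also have to be granted: that the named tests will be applied to heart dose across surgical groups, and that both sides are eligible because side is never restricted. Both are reasonable readings. The objective concerns three techniques, and no other test is named for continuous outcomes.

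It can further be said that this is one variable in a pilot with no decision rule, that planned frequency tables could show side by group, and that Kruskal-Wallis has no error term in the strict sense. The first limits the weight of the point. The second is only partial cover: side is not named and heart dose by side is not planned. The third is a matter of terms, since simulated Kruskal-Wallis power falls in much the same way.

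Finally, the remedy has limits. An additive model assumes similar spread and technique effect on both sides, a rank version gives no adjusted interval in dose units, and no option is well powered if technique acts only on the left. These are reasons to pair the model with a display by side, not to keep the one-factor test.

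**Conclusion.** The concern holds, as a minor one. The plan names only one-factor tests for continuous outcomes, and heart dose is the one listed normal structure not defined relative to the treated side. If those tests compare heart dose across surgical groups, a left-right gap is left unmodelled.

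Under the assumptions above, including side leaves ANOVA power 3 points lower at no gap (59% to 56%), about equal at 0.5 SD, and higher by 7, 24, 36 and 42 points at 1, 2, 3 and 4 SD. Which of these applies cannot be settled from the documents. Overall type I error is not a material problem unless side is related to technique. The electron-versus-photon comparison within each patient is not affected, because a patient's side is the same in both plans.

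**What to change.** For heart dose, replace the one-way test with wording such as:

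> Treated side (left/right) will be tabulated by group. For each plan type, individual heart doses will be shown by group and side, with n, and mean and SD only where a cell has at least 3 patients. In left-sided patients, n, median and range will be given by group. Groups will be compared by ANOVA with technique and treated side as factors (on ranks if skewed), with side-adjusted differences and 95% CIs where the data are not ranked. This analysis is exploratory.

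The cost is a few sentences and one error degree of freedom (17 to 16). Treated side is known for every patient, so no new data are needed and no treatment changes. If side has no effect, the price is the 3 points of power already given and a half-width of 1.20 instead of 1.16 SD. The display of individual doses must accompany the model because it lets the reader judge the additive assumption, and because cell summaries alone would often rest on too few patients.
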